8.1.4 How supplied/Storage and handling**8.1.4.1 How Supplied**

ADCETRIS® (brentuximab vedotin) for Injection is supplied as a sterile, white to off-white preservative-free lyophilized cake or powder in individually-boxed single-use vials:

- NDC (51144-050-01), 50 mg brentuximab vedotin.

8.1.4.2 Storage

Store vial at 2-8°C (36-46°F) in the original carton to protect from light.

8.1.4.3 Special Handling

Procedures for proper handling and disposal of anticancer drugs should be considered. Several guidelines on this subject have been published, and are available in the manufacturer's prescribing information insert. Each study site will be responsible for regular inventory checks and disposing of expired drug in a timely manner

8.1.5 Protocol dose:

1.2 mg/kg IV weekly x 3, then 1.8 mg/kg IV every 3 weeks.

NOTE: A baseline weight and height should be obtained on the first day of treatment for all patients, and weights should be checked at least every three weeks (once per cycle). Treatment dosages will be based upon most recent weight and BSA (preferably from that day of treatment). Dosing is to be subsequently modified if subject weight has changed by more than 10% or the BSA has changed more than 5%.

8.1.6 Instructions for Preparation and Administration

Procedures for proper handling and disposal of anticancer drugs should be considered. Several guidelines on this subject have been published (see manufacturer's prescribing information insert). Use appropriate aseptic technique for reconstitution and preparation of dosing solutions.

8.1.6.1 Reconstitution

Calculate the dose (mg) and number of vials of ADCETRIS® required. The dose for patients with a weight of >100 kg should be calculated for 100 kg. Reconstitute each 50 mg vial of ADCETRIS® with 10.5 mL of Sterile Water for Injection, USP, to yield a single-use solution containing 5 mg/mL brentuximab vedotin. Direct the stream toward wall of vial and not directly at the cake or powder. Gently swirl the vial to aid dissolution. DO NOT SHAKE. Inspect the reconstituted solution for particulates and

discoloration. The reconstituted solution should be clear to slightly opalescent, colorless, and free of visible particulates. Following reconstitution, dilute immediately into an infusion bag, or store the solution at 2-8°C (36-46°F) and use within 24 hours of reconstitution. DO NOT FREEZE. Discard any unused portion left in the vial.

8.1.6.2 Dilution

Calculate the required volume of 5 mg/mL reconstituted ADCETRIS® solution needed and withdraw this amount from the vials. The dose for patients with a weight of >100 kg should be calculated for 100 kg. Immediately add the reconstituted solution to an infusion bag containing a minimum volume of 100 mL to achieve a final concentration of 0.4 mg/mL to 1.8 mg/mL brentuximab vedotin. ADCETRIS® can be diluted into 0.9% Sodium Chloride Injection, 5% Dextrose Injection or Lactated Ringer's Injection. Gently invert the bag to mix the solution. ADCETRIS® contains no bacteriostatic preservatives. Following dilution, infuse the ADCETRIS® solution immediately, or store the solution at 2-8°C (36-46°F) and use within 24 hours of reconstitution. DO NOT FREEZE.

8.1.7 **Route of administration for this study**

Intravenous infusion.

8.1.8 **Incompatibilities:**

Brentuximab vedotin is not to be mixed with, or administered as an infusion with, other medicinal products. (The only exception is that it may be co-administered, but not mixed with, rituximab, when administered as part of this clinical trial.)

8.1.9 **Availability**

Brentuximab vedotin will be supplied by the study supporter, Seattle Genetics. This drug may be ordered by completing the Investigational Drug Request/Shipment Record Form (see Appendix B), which then may be faxed or emailed as directed on the Form.

8.1.10 **Side effects:**

The most common adverse reactions (≥20%), regardless of causality, were neutropenia, peripheral sensory neuropathy, fatigue, nausea, upper respiratory tract infection, diarrhea, pyrexia, and vomiting.

Less commonly progressive multifocal leukoencephalopathy (PML), Stevens-Johnson syndrome (SJS), toxic epidermal necrolysis (TEN), tumor lysis syndrome (TLS), acute pancreatitis, pulmonary toxicity, and hepatotoxicity.

NOTE: Current safety data are based on oncology studies (see section 1.2.1). As a result, 1.8mg/kg is the recommended dose for approved indications.

8.1.11 **Return and Retention of Study Drug**

It is NOT expected that excess drug will be returned to the manufacturer, and it is asked that sites destroy drug remaining at the end of the study per their local policy. The manufacturer will provide memos with lot number and expiration dates, and expired drug may also be destroyed per local policy.

8.1.12 **Nursing/patient implications**

- Avoid use in patients with severe renal impairment
- Avoid use in patients with moderate or severe hepatic impairment (Child-Pugh B or C). .

8.2 Rituximab

8.2.1 Other names for the drug(s)
IDE-C2B8, Rituximab, NSC# 68745

8.2.2 Classification - type of agent
Chimeric murine-derived monoclonal antibody

8.2.3 Mode of action
Rituximab is a chimeric murine/human gamma 1 kappa monoclonal antibody (Chinese hamster ovary [CHO] transfectoma). It recognizes the CD20 antigen expressed on normal B cells and most malignant B-cell lymphomas. It binds with high affinity to CD20-positive cells, performs human effector functions in vitro, and depletes B cells in vivo. The Fab domain of rituximab binds to the CD20 antigen on B-lymphocytes and the Fc domain recruits immune effector functions to mediate B-cell lysis in vitro. The biological effect is manifested by B-cell depletion in peripheral blood, lymph nodes, and bone marrow.

8.2.4 Storage and stability
Rituximab vials are stored at refrigerated temperatures 2° to 8°C (36° to 46°F). Protect vials from direct sunlight. Diluted drug product at a concentration of 0.5 to 4 mg/ml in polyvinylchloride or polyolefin IV bags containing normal saline or dextrose 5% can be stored for up to 24 hours at 2° to 8°C, and at room temperature for an additional 12 hours

8.2.5 Protocol dose
Rituximab will be administered the standard dose of 375 mg/m² IV weekly for the first 4 weeks then every 6 weeks thereafter.

8.2.6 Preparation
Withdraw the necessary amount of rituximab and dilute to a final concentration of 1-4 mg/ml into an infusion bag containing either 0.9% Sodium Chloride or 5% Dextrose in Water. Gently invert the bag to mix the solution. Caution should be taken during the preparation of the drug, as shaking can cause aggregation and precipitation of the antibody

8.2.7 Route of administration for this study
Intravenous infusion (see Section 5 for detailed administration instructions).

8.2.8 Incompatibilities
Do not mix or dilute rituximab with other drugs. No incompatibilities between rituximab and polyvinylchloride or polyethylene bags have been observed.

8.2.9 Availability
Rituximab is commercially available and will not be provided by the study.

8.2.10 Side effects
Adverse events with an incidence > 5% include: fever, chills, rigors, asthenia, headache, angioedema, hypotension, myalgia, dizziness, fatigue, throat irritation, abdominal pain, nausea, abdominal pain, nausea, vomiting, leukopenia, thrombocytopenia, neutropenia, rhinitis, broncospasm, pruritus, rash, urticaria.

8.2.11 Return and Retention of Study Drug
Rituximab will be prescribed to all patients on study. No investigational supply will be purchased or stored for study purposes.

9.0 CORRELATIVES/SPECIAL STUDIES

9.1 The objectives of the correlative studies are to determine:

- 9.1.1 the frequency of expression of both CD30, and markers of EBV (EBER, LMP-1, and EBNA-2), in NHL and solid tumors
- 9.1.2 whether and to what extent CD30 expression, and expression of EBV markers, predict for response and outcome on this prospective trial
- 9.1.3 whether a multivariate model of outcome in PTLD can be prospectively validated, and whether expression of CD30 and EBV markers can be incorporated into a multi-factorial prognostic model for PTLD:
- 9.1.4 whether changes in serum levels of EBV correlate with response and subsequent loss of response to therapy
- 9.1.5 Bank whole blood samples for future, unspecified use (phase II patients only).

9.2 Background and Rationale

The Epstein Barr Virus (EBV) is implicated in the pathogenesis not only of multiple lymphoid malignancies, including Hodgkin and Burkitt lymphoma [32], PTLD [9], peripheral T-cell lymphoma (PTCL) [40], but also of various solid tumors, such as nasopharyngeal carcinoma [41] and possibly breast and gastric cancers [42]. Many of these diseases carry poor prognoses, and even among those with generally good prognoses (eg, HL and BL), there are significant subsets of patients who die due to relapsed or refractory disease.

The membrane glycoprotein CD30 is a tumor necrosis factor receptor, was first identified as a marker of Reed–Sternberg (RS) cells in HL [43], and is universally expressed in this disease. It is also frequently expressed in PTCL and PTLD [9], and in virus-infected lymphocytes and activated T-cells [44]. Increased levels of both membrane-bound CD30, and the soluble form (sCD30), which is generated by proteolytic cleavage of the extracellular component of the molecule, are found in patients infected with EBV and HIV [45]. Increased expression of sCD30 is associated with poor outcome in HIV, ALCL and HL [45-47]. In fact, in both ALCL and HL, levels of sCD30 decrease with treatment and subsequently rise with recurrence [46], [47]. Whereas CD30 expression is not routinely evaluated in other types of non-Hodgkin lymphoma (NHL), nor in solid tumors, it is unclear to what extent such tumors might express CD30.

Taken together, these data highlight interesting questions that have yet to be answered. For instance, it remains unclear to whether and to what extent CD30 expression, and its localization, might predict for response to SGN-35. It is also unknown whether markers of EBV expression and/or proliferation, when associated with malignancy, might predict for response to SGN-35, in correlation with, or irrespective to, CD30 expression.

Prognostication for patients with PTLD has not been well studied. In a large cohort of patients with PTLD, Evens, et al, evaluated primarily clinical features of disease, and reported a multivariate model of PFS and OS, which relied upon the presence vs absence of normal albumin levels, CNS involvement, and bone marrow involvement [12]. This model has not been prospectively validated.

9.2.1 **Objective 1.** Determine the frequency of expression of both CD30, and markers of EBV (EBER, LMP-1, and EBNA-2), in NHL and solid tumors:

Pre-treatment biopsy samples, obtained from pathology archives at NMH, will be identified by a search of corresponding pathological diagnoses in approximately the following numbers:

Non-Hodgkin lymphoma (excluding ALCL) N=100
Diffuse large B-cell lymphoma (DLBCL) N=30
Burkitt lymphoma (BL) N=20
Follicular lymphoma (FL) N=30
Other B-cell lymphoma (mantle cell, marginal zone lymphomas)
N=20
Nasopharyngeal carcinoma N=20
Gastric adenocarcinoma N=20

Each sample will be evaluated by IHC with respect to expression of CD30 and EBV markers (EBER, LMP-1, and EBNA-2). Percentage of positivity will be estimated by an experienced hematopathologist, with values (0-100%) reported both for the malignant lymphoid cells, and for the stromal cells.

This will be a descriptive analysis of the rates of expression of these markers in various disease states, and no formal statistical analysis is planned.

9.2.2 **Objective 2.** Determine whether and to what extent CD30 expression, and expression of EBV markers, predict for response and outcome on this prospective trial:

As described in Objective 1, each sample will be evaluated by IHC with respect to expression of CD30 and EBV markers (EBER, LMP-1, and EBNA-2). Percentage of positivity will be estimated by an experienced hematopathologist, with values (0-100%) reported both for the malignant lymphoid cells, and for the stromal cells.

In univariate and multivariate analyses, these percentages will be correlated with response (CR/PR vs SD/PD), and PFS.

9.2.3 **Objective 3.** Determine whether a multivariate model of outcome in PTLD can be prospectively validated, and whether expression of CD30 and EBV markers can be incorporated into a multi-factorial prognostic model for PTLD:

We will evaluate the model described above [12] in the patients treated as part of this trial. We will additionally incorporate CD30 expression and markers of EBV into a multivariate analysis to determine whether a more precise clinicopathologic model of prediction is possible.

9.2.4 **Objective 4.** Determine whether changes in serum levels of EBV correlate with response and subsequent loss of response to therapy:

Serum EBV levels will be followed as standard of care, and will be evaluated as a dichotomous variable (undetectable vs detectable). Loss of detectable EBV will be correlated with response (CR/PR vs SD/PD), and emergence of detectable EBV will likewise be correlated with loss of response.

9.2.5 **Objective 5.** Peripheral blood samples will be collected will be collected from patients at baseline, day 1 of induction, and day 1 of the first 3 maintenance cycles. This will be stored for future, unspecified use.

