NCI	National Cancer Institute
NHL	Non-Hodgkin Lymphoma
ORR	Overall Response Rate
OS	Overall Survival
PBMCs	Peripheral Blood Mononuclear Cells
PD	Progressive Disease
PFS	Progression Free Survival
p.o.	per os/by mouth/orally
PR	Partial Response
PRR	Partial Response Rate
RP2D	Recommended phase II dose
QOD	Every other day
SAE	Serious Adverse Event
SD	Stable Disease
SGOT	Serum Glutamic Oxaloacetic Transaminase
SPGT	Serum Glutamic Pyruvic Transaminase
WBC	White Blood Cells

STUDY SCHEMA

- DLT period (Phase I only): 21 days of induction
- Duration of treatment (Phase I and II): one year, or until POD (whichever occurs first)
- Primary objective assessment: toxicity after week 4 treatment (Phase I only); scans after induction treatment and/or after consolidation treatment (if applicable) (Phase II only)

*This may be repeated once at discretion of treating investigator; see Section 4.0 (TREATMENT PLAN) for details.

DOSING SCHEMA (in weeks, continued for one year total, or until POD)

STUDY SUMMARY

Title	A Phase I-II Trial of Brentuximab Vedotin Plus Rituximab as Frontline Therapy for Patients with Lymphomas of Immunosuppressed States
Version Date	June 14, 2017 (Amendment 8)
Protocol Number	NU 12H09
Phase	I/II
Methodology	Open-label, single-arm
Study Duration	Approximately 30 months
Study Center(s)	Northwestern University, University of Chicago
Objectives	
Primary objectives: Phase I: Evaluate the safety of brentuximab vedotin and rituximab in patients with immunosuppressed lymphoid malignancies and to determine the recommended phase II dose (RP2D) of the combination. Phase II: Evaluate the efficacy of brentuximab vedotin and rituximab in patients with immunosuppressed lymphoid malignancies.
 
Secondary objectives: Phase II:
 
 1. Further evaluate the frequency and severity of toxicity. 2. Further evaluate the efficacy as measured by one-year PFS and OS. 3. Determine the effects of the combination of brentuximab vedotin and rituximab on markers of EBV activation and proliferation. 4. Further evaluate efficacy as measured by time to initiation of cytotoxic chemotherapy. 5. Further evaluate efficacy as measured by observed rates of graft rejection. 
Exploratory objectives (Phase I and II): Correlate response and outcomes with CD30 expression and EBV markers and levels.

Number of Subjects	Phase I: 3-9 patients; Phase II: 24 patients

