2.3 Primary Endpoints

- 2.3.1 The primary endpoint for phase I, dose-limiting toxicity (DLT) will be defined as the occurrence of toxicity as detailed in section 4.2 (using CTCAE v 4.03), experienced during the first 3 weeks of study treatment. The MTD, which constitutes the RP2D, will be defined as described in Section 11 (Study Design).
- 2.3.2 The primary endpoint for phase II, response after induction or induction/consolidation, will be defined as the detection of SD, PR, or CR by CT or PET/CT, and/or resolution of marrow-only involvement. CR and PR will each be assessed according to the Revised Response Criteria for Malignant Lymphoma. Assessments will be performed after induction and/or consolidation treatment (if applicable).

2.4 Secondary Endpoints:

- 2.4.1 Adverse events will be defined as those included in CTCAE v 4.03. The occurrence and severity of each will be recorded.
- 2.4.2 PFS will be defined as the time elapsed between treatment initiation and tumor progression or death from any cause (whichever occurs first), with censoring of patients who are lost to follow-up. OS will be defined as freedom from death by any cause.
- 2.4.3 Best response will be assessed by CT or PET/CT according to the Revised Response Criteria for Malignant Lymphoma after induction and/or consolidation (if applicable) and every 12 weeks during maintenance treatment.
- 2.4.4 EBV activation and proliferation will be measured by viral loads as measured at time of enrollment and monthly thereafter in all enrolled patients, until completion of study therapy.
- 2.4.5 Time to initiation of cytotoxic chemotherapy will be defined as the time elapsed between treatment initiation, and time of first non-targeted cytotoxic chemotherapy.
- 2.4.6 Graft rejection will be defined as any of the following: documentation of new or progressive rejection by tissue biopsy of the graft; re-transplantation due to graft rejection; clinical diagnosis of new or progressive graft rejection, since start of treatment on protocol, as given by the patient's transplant physician. Escalation of intensity of immunosuppression will not, by itself, be considered evidence of graft rejection. (Note: patients with clinically active graft rejection will not be excluded from trial enrollment, but will not be considered to have treatment-emergent graft rejection unless progression of rejection is documented.)

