2.5 Exploratory Objectives

The objectives of the correlative studies are to determine:

- 2.5.1 whether and to what extent CD30 expression predicts for response and outcome
- 2.5.2 whether and to what extent expression of EBV markers predicts for response and outcome
- 2.5.3 whether changes in serum levels of EBV correlate with response and subsequent loss of response to therapy
- 2.5.4 Collect and store peripheral blood samples for future, unspecified use (phase II patients only).

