2.6 Exploratory Endpoints

Levels of CD30 expression, EBV proliferation, and tumor proliferation (ie, Ki-67), all obtained from TMAs performed on pre-treatment tissue samples, will be correlated with ORR, as well as with EFS at one year. Quantitative serum EBV levels will be monitored for the duration of treatment, and change in levels correlated with ORR, duration of response, and progression of disease.

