10.2 Sample Size and Accrual

For Phase I, we anticipate enrolling either three or six patients, depending on whether one or two cohorts are opened. For Phase II, we plan to enroll 24 patients. This results in a total of 27-33 patients. Under current conditions at our centers, we anticipate being able to successfully accrue patients to this protocol at an average rate of 1.5 per month, resulting in a target time frame of approximately 2-2.5 years for completion of Phases I and II.

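### Sections 9.2.4 and 2.6 set different analyses of serum EBV for the same exploratory objective, and the plan does not say which governs

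*Combined protocol and SAP*

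**What the plan says.** The objective is stated in Section 2.5.3 as finding out "whether changes in serum levels of EBV correlate with response and subsequent loss of response to therapy". Section 9.1.4 and the title of Objective 4 in Section 9.2.4 repeat it. The Study Summary places it in both phases: "Exploratory objectives (Phase I and II): Correlate response and outcomes with CD30 expression and EBV markers and levels".

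Two sections then say how the data will be analysed:

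- Section 2.6: "Quantitative serum EBV levels will be monitored for the duration of treatment, and change in levels correlated with ORR, duration of response", and also with progression.
- Section 9.2.4: serum EBV "will be evaluated as a dichotomous variable (undetectable vs detectable". It continues: "Loss of detectable EBV will be correlated with response (CR/PR vs SD/PD". Emergence of detectable EBV is to be related to loss of response.

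The quantitative data are planned. Under Section 2.4.4, "EBV activation and proliferation will be measured by viral loads as measured at time of enrollment and monthly thereafter in all enrolled patients", and Table 5 has a row for serum EBV viral load. Section 10 contains no EBV analysis. No limit of detection is given, and no text ranks the two analyses or calls either one supportive.

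**The concern.** Two sections of the current text turn one set of measurements into different variables. An analyst could follow either after seeing the data and still be within the plan.

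The rule in 9.2.4 also fits its own objective poorly. The objective concerns changes in level, but the rule registers a change only when the detection limit is crossed. EBV positivity is not an entry requirement (Section 1.3), so some patients may start undetectable and have nothing to lose. Section 9.2.4 does not say whether they are left out or counted as showing no loss. Tissue CD30 and EBV markers, by contrast, are kept as percentages from 0 to 100 in Section 9.2.2.

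At stake is the chance that this correlative aim detects an association in a small trial. No trial decision depends on it.

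**Working it through.** **1. What each section does with typical patients**

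| Course of serum EBV | Section 2.6 (change in level) | Section 9.2.4 (detectable or not) |
|---|---|---|
| Detectable, then undetectable | A fall, bounded by the detection limit | Loss |
| Detectable, large fall, still detectable | Large change | No change |
| Undetectable throughout | No measurable fall | Loss impossible |
| Undetectable, then detectable | A rise | Emergence |

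The second row is where the two sections disagree about the same patient.

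**2. Sample size available**

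The plan gives no sample size, effect size or power for the EBV analysis, so it has no EBV figure to reproduce. Section 10.2 says "For Phase II, we plan to enroll 24 patients" and, for both phases, "This results in a total of 27-33 patients". The 24 does reproduce as the expected size of the optimal two-stage design in Section 10.1.2. With at most 8 of 15 responses stopping stage 1, a maximum of 43 patients and a stopping probability of 0.696 under the null, it is 15 + (1 − 0.696) × (43 − 15) = 23.5. The number with detectable EBV at baseline is not stated.

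**3. Information kept after dichotomising**

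Assume the EBV change is normal and a share p falls on one side of the cut c = Φ⁻¹(p). The efficiency of the binary variable relative to the continuous one is φ(c)² / [p(1 − p)].

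- p = 0.50: 0.3989² / 0.25 = 0.637 (= 2/π), a loss of 36%
- p = 0.70: 0.3477² / 0.21 = 0.576, a loss of 42%
- p = 0.80: 0.2800² / 0.16 = 0.490, a loss of 51%

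The loss passes one half at about p = 0.79.

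| Split | Efficiency | 24 patients act like | 33 patients act like |
|---|---|---|---|
| 50/50 | 0.637 | 15.3 | 21.0 |
| 70/30 | 0.576 | 13.8 | 19.0 |
| 80/20 | 0.490 | 11.8 | 16.2 |

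**4. Power in assumed scenarios**

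The formula ignores both the detection limit and the coarseness of Fisher's test, so power was simulated. Assumptions: 24 patients, all detectable at baseline; about 70% responders; a latent normal response variable correlated with EBV change; values below the limit tied at the limit; 30-85% of patients clearing EBV; two-sided 0.05.

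| Latent correlation | Rank test on change | Fisher's test on clearance |
|---|---|---|
| 0.6 | 0.40-0.59 | 0.14-0.38 |
| 0.5 | 0.28-0.42 | 0.10-0.25 |

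The ranges run over the clearance shares, and the rank test was ahead at every one. A second model (responders shifted by 1.25 SD, no detection limit, which flatters the quantitative analysis) gives about 0.72-0.73 against 0.13-0.49 with 24 patients, and about 0.86-0.87 against 0.38-0.70 with 33.

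**The case against.** The strongest reply is that the sections can be read together: 2.6 covers change in level, and 9.2.4 covers clearance and re-emergence. The aim is exploratory, with no alpha, power claim or decision rule attached, and the choice of test is partly preference. This is fair as far as it goes. It does not answer the point, because both sections serve an identically worded objective and neither mentions the other.

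Patients undetectable at baseline also limit a log-change analysis, since they have no measurable fall, and under 9.2.4 they can still contribute through emergence. This stands. It is why both the change and the clearance analyses need to be confined to patients detectable at baseline.

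Four stronger readings are tempting, and the documents do not support them:

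- *Serum EBV will be analysed only as a binary variable.* That is true of 9.2.4 alone; 2.6 plans a quantitative analysis.
- *Most of the information is lost.* Under the normal model that needs a split beyond about 79/21, and the documents give no detectability rate.
- *The binary test has almost no power.* Fixing 17 responders and 7 non-responders against a 12/12 split gives Fisher power of about 0.15 at correlation 0.6 and 0.08 at 0.5. In that table, a 6-to-1 division of the non-responders gives p = 2 × (6,188 + 7 × 12,376) / 2,704,156 = 0.069, so only 7-to-0 is significant. Let the responder count vary around 70% and the median-split figures rise to about 0.29 and 0.19.
- *Differences between assays cannot matter, because each patient is their own control.* Section 9.2.4 has EBV followed as standard of care, and nothing says that a patient's laboratory or assay stays the same.

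Tying values at the detection limit also reduces the power of the rank test. The figures in the first power table already include this, and the gap narrows but remains.

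**Conclusion.** The point holds as an unresolved conflict between 9.2.4 and 2.6. The binary rule is the less informative of the two: it costs over a third of the information even at its most favourable split, and power was lower in every scenario examined.

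The conflict itself rests on the text alone. The size rests on assumptions that the documents cannot confirm: normality, the latent correlation, the clearance share, a consistent assay within patient, and 24 patients all detectable at baseline. The objective spans both phases (27-33 patients) and the detectable number is unknown, so the informative sample could be smaller or larger than 24. The power figures illustrate the comparison and do not predict this trial's results.

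This is a minor but worthwhile correction to an exploratory aim. The primary endpoint and the trial's error rates are unaffected.

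**What to change.** Amend Section 9.2.4 to agree with 2.6:

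- **Main analysis:** within-patient change in log10 viral load, compared between CR/PR and SD/PD by a rank test, in patients detectable at baseline.
- **Detection limit:** state it. Set values below it at the limit and treat them as tied in the ranking.
- **Supportive analyses:** loss of detectable EBV in patients detectable at baseline, and emergence of detectable EBV against loss of response.
- **Repeated measures:** any model of EBV over time should be descriptive at most. With 27-33 patients and an unknown number of relapses it may not be estimable.
- **Assay:** record the assay used for each patient, because the main analysis assumes that it does not change within patient.

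The cost is a wording change plus recording the assay. Viral loads are already scheduled under Section 2.4.4 and Table 5, so no extra samples are needed. The one small downside is that a detection-limit convention has to be chosen and fixed before the data are examined.
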